3.2.1.2. Secondary efficacy analysis

The secondary efficacy analyses will be performed on the ITT population. In these analyses, no interaction will be tested for EFS, OS, disease-specific mortality and PSA doubling time. For serum testosterone, only patients in the triptorelin-treated group will be included in the analysis

3.2.1.2.1. Event-Free Survival

EFS will be provided by treatment group (cf. Section 3.2.10 for derived EFS).
EFS will be compared between groups using the same analysis and strategy used for BRFS.

3.2.1.2.2. Overall Survival

OS will be provided by treatment group (cf. Section 3.2.10 for derived OS).
OS will be compared between groups using the same analysis and strategy used for BRFS.

3.2.1.2.3. Disease-specific mortality

Disease-specific mortality will be provided by treatment group (cf. Section 3.2.10 for derived disease-specific mortality).
Disease-specific mortality will be compared between groups using the same analysis and strategy used for BRFS.

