1. INFORMATION TAKEN FROM THE PROTOCOL

1.1. Study objectives

1.1.1. *Primary objective*

To assess the benefit of immediate adjuvant chemical castration after radical prostatectomy (RP) in patients with high-risk prostate cancer expressed as biochemical relapse-free survival (BRFS).

1.1.2. *Secondary objectives*

[figure not shown]
To compare the two groups in terms of:

- Event-Free Survival (EFS), Overall Survival (OS), Disease Specific-mortality rate and prostate specific antigen doubling time (PSADT)
- Impact on health-related quality of life (HRQoL)

To assess overall safety of immediate chemical castration.

1.1.3. *Ancillary Exploratory objectives*

CCI

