RAP Final Version 3 [22-JUL-2019]

15/248

CCI

1 Adverse events (AEs) will only be collected until Visit 5/Month 9; this corresponds to three months after the last triptorelin injection for those patients in the triptorelin group. After this visit, only AEs and SAEs related to triptorelin according to Investigator's judgement should be reported (with the exception of AEs resulting in death that should be reported until the end of the study).

Patients will not be withdrawn from the study if study medication is discontinued. Follow-up will continue for all patients every 3 months and for at least 36 months.

1.3.4. *Planned sample size*

It is planned to recruit 226 patients in approximately 10 centres in two countries (China and Russia) according to the Sample Size Determination.

The sample size estimation was based on the primary efficacy endpoint of BRFS. Assuming that with RP alone, the probability of biochemical (PSA) relapse as defined in Section 4.2.1 of the study protocol at 36 months after RP is 40% in high-risk patients (Section 2.1 of the study protocol, Table 1), and anticipating that immediate adjuvant hormonal therapy added to RP will reduce this probability to 20% (percentage considered to be clinically relevant), 113 patients per treatment group (226 in total) are required in order to detect such a difference using a two-sided log-rank test at a significance level of 5% and a power of 90%, assuming a common 1% exponential dropout rate (corresponding to an approximate 5% dropout rate per year).

These 226 patients are required to observe 61 BR in order to achieve 90% power. For patients with no sign of disease progression at 36 months post-randomisation, monitoring will continue until the 61 BR events are observed at the study global level. If the 61 events are observed before all patients complete the 36 months post-randomisation monitoring period, the study will be continued until those patients reach their 36 month visit (Visit 14).

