3.1.2. Secondary efficacy endpoint(s)

The secondary efficacy endpoints are:

- EFS (defined for each patient as the period of time (in months) from randomisation to time of first clinical disease progression or death from any cause).
- OS (defined for each patient as the period of time (in months) between randomisation and death from any cause).

- Disease-specific mortality (measured as the time (in months) between randomisation and death related to prostate cancer).
- PSADT (defined as the time (in months) from the first documented PSA increase >0.2 ng/mL to the time of the first value more than twice that of the first increased value).
- PSA level at each visit.
- Serum testosterone in the triptorelin treatment group at baseline, 3, 6 and 9 months.
- HRQoL (assessed using the Assessment of Cancer Therapy – Prostate (FACT-P) questionnaire, version 4, and the 36-item short form (SF-36) health survey, version 2) in both treatment arms at baseline, 9, 24 and 36 months.

3.1.3. *Safety endpoint(s)*

The safety endpoints are:

- Signs and symptoms, incidence and severity of all AE(s) regardless of relationship to the study drug graded according to the NCI-CTCAE version 4.0 scale including SAEs and treatment discontinuations due to toxicity.
- Clinical laboratory tests
- Concomitant medications and non-drug therapies
- Concomitant and surgical procedures

3.1.4. *Multiplicity*

No adjustment for multiplicity will be performed.

3.1.5. *Significance testing and estimation*

All statistical tests will be performed two-sided with a type I error rate set at 5%.

Quantitative variables will be summarised in statistical tables indicating the number of non missing observations (n), the mean and standard deviation (SD), the two-sided 95% confidence interval (CI) of the mean, the median, the quartiles (Q1 and Q3), the minimum and maximum.

Qualitative variables will be summarised in statistical tables indicating the number of non missing observations (n), frequency, percentage of each modality and the two-sided 95% CI associated.

For all parameters, the number of missing values will also be reported in the tables, but they will not be counted for the percentage calculation (qualitative data).

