Time to event data will be analysed using Kaplan-Meier method to obtain the estimates of survival median, their associated 95% CI, survival curves for each treatment group and log-rank test p-value will be provided for treatment comparison. The Cox Proportional hazard model will be fitted to compute hazard ratios and the corresponding 95% CI.

All quantitative variables will be analysed with either analysis of variance (ANOVA) or analysis of covariance (ANCOVA) adjusting for baseline when measured. Treatment effect estimates (differences between treatment groups) will be provided with their associated 95% CI.

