Compliance

Time between first drug administration and RP (weeks) will be derived as $(\text{Date of first drug administration} - \text{Date of radical prostatectomy} + 1) / 7$.

Time between each drug intake (weeks) will be derived as $(\text{Date of drug intake at Visit } t - \text{Date of drug intake at visit } t-1 + 1) / 7$.

Partial dates of treatment will be imputed to calculate times:

- If the day is missing and month is present the 15 of the month will be used.
- If year is present and day and month are missing then the difference between years will be used.

Changes from baseline

Changes from baseline will be calculated as a difference from baseline (e.g. assessment at the visit – assessment at baseline).

Length of patient exposure in the study

Length of patient exposure in the study (months) will be calculated as [(Date of last visit attended – informed consent date) + 1] / 30.4375.

Duration of study drug exposure

Duration of study drug exposure (months) will be calculated as [(Date of last drug administration – Date of first drug administration) / 30.4375] + 3.

Adverse event

Time to onset of AE (days) = AE start date – date of randomisation.

Duration of AE (days) = (AE resolution date – AE start date) + 1.

Time-to-event criteria

BRFS (months) will be derived as (Date of first BR – date of randomisation + 1) / 30.4375.

EFS (months) will be derived as (Date of clinical disease progression or death from any cause – date of randomisation + 1) / 30.4375.

OS (months) will be derived as (Date of death from any cause – date of randomisation + 1) / 30.4375.

Disease specific mortality will be derived as (Date of death related to prostate cancer – date of randomisation + 1) / 30.4375.

PSADT (months) will be derived as (Date of sample when the first PSA value > than twice that of the first increased value – Date of sample of the first PSA value increased value (i.e. > 0.2 ng/mL) + 1) / 30.4375.

All of these time-to-event variables will be rounded to 1 decimal.

For BRFS, EFS, OS and Disease specific mortality, if the date of event or censor is prior to the date of randomisation, the data of event or censor taken into account will be the date of randomisation.

Rules for time-to-event data

The following table defines the rules for censoring data (for Kaplan-Meier analysis)

- BRFS

Event	Decision	Date of event or censor to consider for analysis
BR	Not censored	Date of BR (i.e. date of the first elevated PSA measurement is >0.2 ng/mL*)

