Event	Decision	Date of event or censor to consider for analysis
Clinical disease progression or death from any cause	Not censored	Date of clinical disease progression or death
No clinical disease progression and no death and no premature withdrawal from the study	Censored	Date of last visit
No clinical disease progression no death and patient premature withdrawal from the study or lost to follow-up	Censored	Date of withdrawal from the study or last contact

- OS

Event	Decision	Date of event or censor to consider for analysis
Death from any cause	Not censored	Date of death
Patient alive and no premature withdrawal from the study	Censored	Date of last visit
Patient premature withdrawal from the study or lost to follow-up	Censored	Date of withdrawal from the study or last contact

- Disease-specific mortality

Event	Decision	Date of event or censor to consider for analysis
Death related to prostate cancer	Not censored	Date of death
Death not related to prostate cancer	Censored	Date of death
Patient alive and no premature withdrawal from the study	Censored	Date of last visit
Patient premature withdrawal from the study or lost to follow-up	Censored	Date of withdrawal from the study or last contact

- PSADT

Event	Decision	Date of event or censor to consider for analysis
First PSA value > than twice that of the first increased value (> 0.2 ng/mL)	Not censored	Date of sample when the first PSA value > than twice that of the first increased value
No PSA value 2 times higher than the first increased value or no increased value and no premature withdrawal from the study	Censored	Date of last evaluable sample
Patient premature withdrawal from the study or lost to follow-up	Censored	Date of last evaluable sample before withdrawal from the study or last contact

Incomplete dates for time-to-event analyses will be handled as follows:

- If the day of the randomisation is missing and month is present, the 15 of the month will be used.
- If the day of the BR, clinical progression or death is missing and month is present, the 01 of the month will be used.
- If the month (or the date) of the death is missing, the date of the last contact will be used.
- The other dates with missing month will be studied case by case.

Castrated patients

A patient will be considered as:

- Castrated if the testosterone level is inferior to 50 ng/dL for the test or confirmation test.

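### Disease-specific mortality is summarised by Kaplan-Meier with other-cause deaths censored, so the mortality-rate objective gets no suitable absolute estimate (small effect, cheap fix)

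*SAP*

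**What the plan says.** Four parts of the SAP together fix this analysis.

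- **Objective (section 1.1.2).** The two groups are to be compared on, among other things, the "Disease Specific-mortality rate".
- **Endpoint (section 3.1.2).** "Disease-specific mortality (measured as the time (in months) between randomisation and death related to prostate cancer".
- **Method (sections 3.1.5, 3.2.1.1 and 3.2.1.2.3).** The general rule is that "Time to event data will be analysed using Kaplan-Meier method to obtain the estimates of survival median", with the 95% CI, curves per arm, a log-rank p-value and Cox hazard ratios. For this endpoint, "Disease-specific mortality will be compared between groups using the same analysis and strategy used for BRFS". The BRFS section adds the number of events per arm. It names no survival or mortality estimate at a fixed time.
- **Censoring (section 3.2.10, rules for time-to-event data).** The rules are introduced by "The following table defines the rules for censoring data (for Kaplan-Meier analysis". In the disease-specific mortality table the row "Death not related to prostate cancer" is censored at the date of death.

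The SAP text mentions no cumulative incidence function and no other competing-risk method. The SAS code is redacted and the output shells are not in the public text, so this point rests on the prose and the censoring tables.

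**The concern.** A man who dies of another cause can no longer die of prostate cancer. Kaplan-Meier treats him like a man lost to follow-up, whose later risk is represented by those still under observation. The complement of the curve therefore describes prostate-cancer mortality in a hypothetical setting where nobody dies of anything else. It does not give the proportion of these patients who die of prostate cancer.

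A reader of the objective would expect that proportion for each arm. The plan offers a curve that overstates it, a median that very likely cannot be estimated, and a raw event count that ignores unequal follow-up. What is at stake is the absolute description of one secondary endpoint. The primary analysis and the between-group test are not affected.

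**Working it through.** **The plan's own figures.** The SAP states no figure for prostate-cancer or other-cause mortality. Its only event probabilities concern biochemical relapse ("at 36 months after RP is 40% in high-risk patients", against 20% with treatment, section 1.3.4). The design built on them reproduces: HR = ln(0.8)/ln(0.6) = 0.437, and the two-sided Schoenfeld formula gives 4 × (1.960 + 1.282)² / (ln 0.437)² = 61.3 events, against 61 stated. Nothing below changes that.

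**Direction of the bias.** At each prostate-cancer death, Kaplan-Meier adds (net survival from prostate cancer just before) × (deaths / number at risk). Aalen-Johansen adds (survival from all causes just before) × (the same fraction). All-cause survival is never the larger of the two, and it is strictly smaller after the first other-cause death. So 1 − KM exceeds the cumulative incidence whenever an other-cause death precedes a later prostate-cancer death. This holds whatever the rates.

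**Size, with assumed constant hazards.** Let a be the yearly hazard of prostate-cancer death, b that of other-cause death, and t the years of follow-up.

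- 1 − KM = 1 − exp(−a·t)
- Cumulative incidence = a/(a+b) × [1 − exp(−(a+b)·t)]

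| a | b | t | 1 − KM | Cumulative incidence | Excess (points) | Relative |
|---|---|---|---|---|---|---|
| 0.01 | 0.02 | 3 | 1 − exp(−0.03) = 2.96% | ⅓ × [1 − exp(−0.09)] = 2.87% | 0.09 | 3% |
| 0.01 | 0.02 | 5 | 1 − exp(−0.05) = 4.88% | ⅓ × [1 − exp(−0.15)] = 4.64% | 0.23 | 5% |
| 0.01 | 0.04 | 5 | 4.88% | ⅕ × [1 − exp(−0.25)] = 4.42% | 0.45 | 10% |

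The excess is taken before rounding. The horizons come from section 1.2.2: at least 36 months per patient, and about 60 months for the whole study including 2 years of recruitment.

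**Wider range.** Let the probability of death by the horizon, in the absence of the other cause, run from 1% to 10% for prostate cancer and from 2% to 20% for other causes. The excess then runs from 0.01 to 1.02 points, or about 1% to 12% relative. The largest absolute excess is at 10% and 20%: 10.00% against 8.98%.

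**Simulation.** The set-up was 113 per arm, 24 months of accrual, a 60-month study and 5% dropout per year. The ratio of 1 − KM to Aalen-Johansen was 1.02 with net probabilities of 2% and 5%, 1.05 with 5% and 10%, and 1.11 with 10% and 20%. These scenarios gave about 1.6, 3.9 and 7.5 prostate-cancer deaths per arm.

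**Against sampling error.** With 113 per arm and no allowance for censoring, the standard error at 3 years is √(0.0287 × 0.9713 / 113) = 1.6 points. At 5 years it is √(0.0464 × 0.9536 / 113) = 2.0 points. The excess of 0.09 or 0.23 points is far smaller.

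**The median.** For the Kaplan-Meier median to fall within 5 years, a would have to be at least ln 2 / 5 = 0.139 per year, about 14 times the assumed 0.01.

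**The case against.** The strongest reply is that the sentence in section 3.2.1.2.3 concerns the comparison between groups, and that comparison is sound. Log-rank and Cox with other-cause deaths censored are standard inference on the cause-specific hazard. If the word rate in the objective means that hazard, the censoring is what one would want. This stands. A reader might infer that the test or hazard ratio is biased, but the documents do not support that.

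A reader might also infer that a biased mortality percentage will be reported. The SAP names medians, curves and event counts, and no 1 − KM figure at a fixed time. The overstatement arises only when someone reads a probability off the curve. This stands too, but it also shows the gap: no usable absolute estimate is named.

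A third tempting inference is that fewer prostate-cancer deaths could be offset unnoticed by other deaths. That goes too far. Overall survival is compared in the same ITT population by the same methods (section 3.2.1.2.2), EFS counts death from any cause, and deaths are listed (section 3.2.2.1). Other-cause death by arm is not shown as an efficacy outcome of its own, so the view of an offset is partial rather than absent.

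Finally, the effect is likely to be small. Follow-up is about 3 to 5 years. Men with a life expectancy under 5 years or significant comorbidity are excluded, and ECOG status must be 0 or 1. Nothing in the SAP supports the 4% per year other-cause scenario, which serves only as an upper illustration. This limits the importance of the point but does not remove it.

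**Conclusion.** The point holds as a minor one about estimation. With other-cause deaths censored, the Kaplan-Meier curve overstates each arm's actual probability of prostate-cancer death, and the median is very unlikely to be reached. The mortality-rate objective is therefore left without a suitable absolute estimate.

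The direction is certain once an other-cause death precedes a later prostate-cancer death. The size rests on assumed rates. At 1% and 2% per year it is about 0.1 points at 3 years and 0.2 at 5 years, and it approaches 1 point only near 10% prostate-cancer and 20% other-cause mortality. The log-rank test, the Cox hazard ratio, the primary analysis and the sample size are unaffected.

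**What to change.** In section 3.2.1.2.3, replace or supplement the Kaplan-Meier curve and median with the Aalen-Johansen cumulative incidence of prostate-cancer death, treating other-cause death as a competing event. Show the cumulative incidence of other-cause death beside it. Report both per arm, at 36 months and at end of study, with 95% CI.

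Keep the log-rank test and Cox hazard ratio with their present censoring, and label both as cause-specific. In the section 3.2.10 table, note that deaths not related to prostate cancer are censored for the cause-specific analyses and coded as competing events for the cumulative incidence.

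The cost is a few lines of SAP text and one additional standard SAS analysis. No new data are needed, because the censoring table already separates the two kinds of death.

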3.2.1.2.4. PSA Doubling Time

PSADT will be provided by treatment group (cf. Section 3.2.10 for derived PSADT).
PSADT will be compared between groups using the same analysis and strategy used for BRFS.

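### PSADT gets a between-arm log-rank test and Cox hazard ratio, although it has a start date only after a PSA rise that treatment is meant to prevent; patients without a rise are censored with no time origin

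*SAP*

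**What the plan says.** SAP 3.1.2 gives the starting point: "PSADT (defined as the time (in months) from the first documented PSA increase >0.2 ng/mL". The clock stops at the first later value more than double that one. The formula in 3.2.10 uses the same two dates and offers no other start date.

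On the analysis, 3.2.1.2.4 states that "PSADT will be compared between groups using the same analysis and strategy used for BRFS". Under 3.2.1.1 that strategy is a two-sided log-rank test, Kaplan-Meier medians and a Cox model with hazard ratio. Section 3.1.5 adds: "All statistical tests will be performed two-sided with a type I error rate set at 5" per cent. Section 3.2.1.2 excludes interaction tests for PSADT but changes nothing else, and places the secondary efficacy analyses on the ITT population.

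The PSADT censoring table in 3.2.10 does not limit the analysis to patients with a rise. Its second row explicitly includes patients who never had a raised value and censors them at the last evaluable sample. Its third row (withdrawal or loss to follow-up) is not limited to patients with a rise either.

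Comparing the groups on PSADT is a secondary objective (1.1.2). The SAP does not call the result descriptive or non-randomised.

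**The concern.** A patient acquires a PSADT only by having a PSA rise after randomisation, and the trial is designed on the expectation that triptorelin halves that event. Patients with a rise in one arm are therefore not the randomised counterparts of those in the other. If relapse risk is related to growth rate, the two groups can differ in doubling time even when treatment does nothing to growth after the rise.

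The text also contradicts itself. By the formula, patients who never rise have no PSADT and drop out. By the censoring table and the ITT rule, they stay in, with a censoring date but no start date. A programmer would have to pick an origin, and randomisation is the obvious candidate. The two readings can push the result in opposite directions, so a secondary objective could be answered with a p-value and hazard ratio whose sign depends on an unstated programming choice.

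**Working it through.** **1. The plan's own figure.** Inputs from SAP 1.3.4:
- Surveillance relapse: "at 36 months after RP is 40% in high-risk patients".
- Triptorelin: "immediate adjuvant hormonal therapy added to RP will reduce this probability to 20" per cent.
- Test: "using a two-sided log-rank test at a significance level of 5% and a power of 90" per cent.
- Size: "113 patients per treatment group (226 in total) are required" and "These 226 patients are required to observe 61 BR in order to achieve 90% power".

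Hazard ratio = ln(0.8)/ln(0.6) = 0.437. Schoenfeld events = 4 × (1.960 + 1.282)² / (ln 0.437)² = 61.3, and the power with 61 events is 0.899. The stated 61 is reproduced.

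**2. How many patients get a start date.** Monthly hazards are −ln(0.6)/36 = 0.01419 and −ln(0.8)/36 = 0.00620. Dropout at the stated 5% per year is −ln(0.95)/12 = 0.00427. The probability of an observed relapse by 36 months is λ/(λ+δ) × (1 − exp(−36(λ+δ))):
- Surveillance: 0.373 × 113 = 42.2
- Triptorelin: 0.186 × 113 = 21.0

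The total is about 63 of 226 (28%), split 2:1 by an event that treatment affects. These are relapse counts. PSADT as worded mentions no confirmation, so patients with any rise could be somewhat more numerous.

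**3. Size of the false signal.** Simulation with 113 per arm, 36 months, PSA every 3 months, 5% per year dropout and relapse fixed at 40% against 20%. **Treatment has no effect on doubling time.** Assumptions not in the SAP: log-normal doubling time, median 6 or 12 months, log SD 0.7, and a link to relapse through a shared factor with log-hazard SD 0 (none), 0.7 (moderate) or 1.5 (strong). There were 1,500 trials per row. Entries are rejection rates of the unadjusted 5% log-rank test.

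| Link | Median (months) | Only patients with a rise (for / against triptorelin) | Never-risen kept, timed from randomisation (all for triptorelin) |
|---|---|---|---|
| None | 6 | 5.0% (2.4 / 2.6) | 82.3% |
| None | 12 | 5.2% (2.2 / 3.0) | 71.4% |
| Moderate | 6 | 6.9% (1.3 / 5.6) | 82.9% |
| Moderate | 12 | 6.9% (1.1 / 5.7) | 76.7% |
| Strong | 6 | 15.3% (0.3 / 14.9) | 84.5% |
| Strong | 12 | 17.3% (0.2 / 17.1) | 79.5% |

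Components may not add exactly because of rounding. With the strong link, the average of the trial medians of true doubling time among patients with a rise was 3.54 months on surveillance against 2.95 on triptorelin (7.07 against 5.88 for the longer assumed median). That difference is selection alone.

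**4. Checks (800 trials each).** With no effect on relapse, rejection was 4.0-6.8% in patients with a rise and 4.4-5.2% with never-risen patients kept. If treatment only delays relapse (strong link, median 6 months), rejection was 8.3% and 27.9% for a 12-month delay, and 13.6% and 63.5% for an 18-month delay.

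The Monte Carlo standard error near 5% is √(0.05 × 0.95/1500) = 0.6 points, or 0.8 points with 800 trials. The moderate-link 6.9% is therefore a small excess; its lopsided split (about 1% against nearly 6%) is the clearer sign. The strong-link and right-hand-column results are far outside simulation error.

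**The case against.** The strongest defence has four parts.

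- The SAP specifies ITT and explicitly carries patients without a rise as censored, so it does not simply discard non-relapsers. That is correct. A reader might infer that the plan is a relapsers-only comparison that would make triptorelin look as if it speeds PSA doubling. The documents do not support that stronger reading, because the censoring table points the other way and, on the obvious origin, the error favours triptorelin. What remains is that the table and the formula cannot both be applied.
- If relapse risk is unrelated to doubling time, the comparison among patients with a rise keeps its 5% error rate. This stands, and the first two rows of the table show it. The SAP gives no information on the link. A reader might infer false-positive rates well above 17% by assuming that relapse is prevented mainly in slow-growing disease; nothing in the SAP establishes that mechanism.
- The secondary objective asks for a comparison on PSADT, so removing the test leaves it unanswered as worded. This is a real cost. An endpoint timed from randomisation gives a valid comparison, but of a different quantity.
- PSADT is one of several secondary endpoints. This is true and limits the consequence.

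**Conclusion.** The concern holds in this form: PSADT as defined does not support a randomised between-arm test of PSA growth, and the SAP fixes neither one analysis set nor one time origin for it.

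The direction and size of the error depend on the reading. Among patients with a rise, false rejection is about 5% with no link, 7% with a moderate link and 15-17% with a strong link, the excess falling against triptorelin. With never-risen patients timed from randomisation, it is 71-85% in favour of triptorelin, because the test then mostly repeats the comparison of relapse incidence.

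These rates rest on the plan's relapse and dropout figures and on assumed doubling times and link strengths. They describe the unadjusted log-rank test; the Cox model adjusted for country, centre and Gleason score was not simulated. The structural point needs none of these assumptions. The primary BRFS analysis and the sample size are unaffected. The SAP should be changed, but the matter does not threaten the main result.

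**What to change.** Amend 3.1.2, 3.2.1.2.4 and the PSADT formula and censoring table in 3.2.10 together:

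1. Define PSADT only for patients with a PSA above 0.2 ng/mL after randomisation, and state whether that rise must be confirmed; BR in 1.3.2.1 requires confirmation, while the PSADT wording is silent. Remove patients without a rise from the second censoring row and limit the withdrawal row to patients with a rise. Report Kaplan-Meier medians with 95% CI by arm, label them descriptive and non-randomised, and drop the log-rank p-value and hazard ratio.
2. For the between-group comparison, analyse in all ITT patients the time from randomisation to the first PSA more than twice the first value above 0.2 ng/mL, censoring patients without that event at their last evaluable sample. State that this endpoint combines relapse with doubling and overlaps with BRFS. A difference on it may come from fewer or later relapses and should not be reported as an effect on PSA growth.

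The cost is SAP wording and one additional derived variable from PSA data already collected. The trial loses the p-value for PSADT as now defined, and the secondary objective should be reported with that limit stated.
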